5. PATIENT SELECTION

5.1. Inclusion Criteria

1. Hospitalization for confirmed PCR positive COVID-19 infection
2. Active cancer, defined as a solid malignancy either undergoing active therapy, receiving therapy within 1 year, or a hematologic malignancy under active therapy or observation.
3. Age ≥ 18
4. Patients with evidence of pulmonary involvement who meet any of the followings; presence of infiltrates on chest X-ray or CT scan or need for supplemental oxygen $< 8\text{L}$ nasal cannula or pulse oximetry $< 94\%$ on room air.
5. Biochemical values within the following limits:
 - a. Creatinine clearance $\geq 25 \text{ ml/min}$ by Cockcroft-Gault equation

- b. Total bilirubin $\leq 1.5 \times$ upper limit of normal (ULN) unless bilirubin rise is due to Gilbert's syndrome or of non-hepatic origin
- c. Alanine aminotransferase (ALT) and aspartate aminotransferase (AST) $\leq 3 \times$ ULN
- 6. Hematology values must be within the following limits (no need to hold growth factors or transfusions):
 - a. Absolute neutrophil count (ANC) $\geq 1000/\text{mm}^3$ independent of growth factor support
 - b. Platelets $\geq 50,000/\text{mm}^3$
- 7. Ability to swallow capsules or receive opened capsule content via nasogastric or enteral feeding tube as described in 7.2
- 8. Ability to provide informed consent indicating that they understand the purpose of and procedures required for the study, including biomarkers, and are willing to participate in the study. If a patient is unable to provide informed consent (e.g. does not possess decisional capacity), a legally authorized representative may provide consent for the patient.
- 9. Women of childbearing potential and men who are sexually active must be practicing a highly effective method of birth control during and after the study consistent with local regulations regarding the use of birth control methods for subjects participating in clinical trials. Men must agree to not donate sperm during and after the study. For females, these restrictions apply for 1 month after the last dose of study drug. For males, these restrictions apply for 3 months after the last dose of study drug.
- 10. Women of childbearing potential must have a negative serum (beta-human chorionic gonadotropin [β -hCG]) or urine pregnancy test at Screening. Women who are pregnant or breastfeeding are ineligible for this study.

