12. STUDY CALENDAR^A

	Screening	Cycle 1 Day 1 ^I	Cycle 2 Day 1 ^I	End of Treatment (day 14 + up to 3 days if outpatient)	1 month post enrollment ^J	2 months post enrollment ^J	3 months post enrollment ^J	6 months post enrollment ^J	12 months post enrollment ^J
Informed Consent	X								
Medical History	X		X		X	X	X	X	X
Concomitant Medications	X	X	X	X	X	X	X	X	X
Adverse Events	X	X	X	X	X	X ^K	X ^K	X ^K	X ^K
Physical Exam	X	X	X	X					
Vital Signs^B	X	X	X	X					
EKG^C	X	X	X	X					
CBC with differential	X	X	X	X	X	X	X	X	X
Serum Chemistry^D	X	X	X	X	X	X	X	X	X
PT/PTT/INR, D- dimer, fibrinogen, LDH	X	X	X	X	X				
Hepatitis B,C Screening^E	X								
CRP, ferritin, troponin	X	X (daily)	X (daily)	X	X				
IL6, IFNγ, TNF	X		X	X					
Serum or Urine Pregnancy Testing	X								
Flow cytometry (Immunome)	X		X	X					
Total serum IgG, IgA, and IgM	X			X		X	X	X	X
Nasopharyngeal SARS-CoV-2 PCR^F	X			X	X (if negative will stop)	X (if negative will stop)	X (if negative will stop)		X (if negative will stop further testing)

Ibrutinib for COVID 19

					Further testing)	Further testing)	Further testing)		
Peripheral Blood for Correlative Laboratory Studies⁶	X	X	X	X	X	X	X	X	X
Ibrutinib or placebo			X						

- A. All research coordinator contact (consent, adverse events, concomitant medications) will be either by phone or over videoconference. Physical examination will be performed by the inpatient treatment team and does not have to be study personnel. For study participants who are discharged prior to completing 14 days, no daily labs will be performed at the outpatient setting and C2D1 labs will be performed on the day of discharge. Study participants will follow institutional inpatients/outpatient isolation initiation and discontinuation measures.
- B. Should include Oxygen saturations and O2 requirement. Consider continuous cardiac monitoring, especially for patients receiving concomitant medications with cardiac effects
- C. Consider continuous cardiac monitoring, especially for patients receiving concomitant medications with cardiac effects. All patients receiving hydroxychloroquine will be placed on telemetry as part of our standard institutional practice guidelines.
- D. Includes chem 10 and liver function panel. Should consider doing chemistry panel and CBC daily.

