Design and Sample Size: Based on a study in China, we assume that the event rate is 40% with standard care and that the event rate can be reduced to 15% when Ibrutinib is added to standard care for COVID-19. With 60 patients and using a standard group sequential design, there is 82.8% power to detect a reduction in the event rate under the alternative hypothesis and constraining the one-sided type I error to 20%. Power was calculated using a z-test for the difference in two proportions, pooled variance, and adjustment for small sample sizes with the Casagrande-Pike-Smith correction (EAST v6.5; Cytel, Inc). There will be an interim analysis when 50% of randomized patients have been followed for 30 days from registration. The study will be stopped early if at the interim analysis the observed event rate is higher in the ibrutinib arm (Arm A) than in the control arm (Arm B). We will plan to over-accrue by about 10% for a total accrual goal of 66 patients.

Although the actual reduction in the event rate could be larger than 25%, it could also be as low as 20% and still be quite meaningful. Furthermore, there is uncertainty in the event rate of the control arm. For these reasons, we have incorporated increased flexibility at the time of the interim analysis to potentially increase the sample size if conditional power indicates promising results, and will thus implement an adaptive group sequential design (Chen, DeMets, Lan; 2004).

At the interim analysis, there are 4 possible outcomes: 1) the futility criteria are met and the trial stops early; 2) the conditional power is unfavorable ($<50\%$), and enrollment continues to the planned sample size without an increase in sample size; 3) the conditional power is in a promising zone (defined as conditional power $\geq 50\%$ and $< 82.8\%$), and sample size may be re-estimated with the original sample size updated to boost the power to a target of 82.8%, subject to a maximum sample size of 120; or 4) the conditional power is favorable ($\geq 82.8\%$), and enrollment continues to the planned

sample size without an increase in sample size. When using this procedure, no adjustment to the final test statistic or critical value from the original design is required to control the Type I error rate. In addition, if the conditional power is in the promising zone, we can choose not to increase the sample size beyond what was originally planned or by a flexible amount without penalty.

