Primary Endpoint Analysis: All randomized patients will be included in the primary endpoint analysis and analyzed in the treatment arm to which they were randomized (ITT population). The data will be analyzed using a one-sided Fisher's exact test and a promising signal declared if $p \leq 0.20$ and the event rate is lower in the experimental arm. Since the primary endpoint is to be measured within the first 30 days of registration, we do not expect that primary endpoint information will be missing. However, if there is data missing, the patient will be considered a treatment failure.

Sensitivity analyses include comparison between treatment arm when adjusting for stratification factors and other important variables such as type of cancer or more refined categories of standard of care therapy via logistic regression. If there are events for respiratory failure based on clinical diagnosis without an objective measure and driven solely by resource limitation or if patient has DNI (Do Not Resuscitate) status, a sensitivity analysis will compare arms excluding patients with these events. Sensitivity analyses will be performed for the ITT population and for eligible patients who receive their assigned therapy without a major protocol violation.

Adverse Event Stopping Rules: If there is no concerning safety signal in the lead-in cohort, and the study is able to continue to the randomized component as planned, we have included a plan for comparing toxicity at the interim analyses (first 30 patients across both arms). Accrual will be temporarily suspended to this study and discussion of the data with co-investigators and the data safety monitoring board will occur if we observe adverse events that satisfy the following criteria:

- If the percentage of grade 3/4 all-cause adverse events is at least 15% higher in the ibrutinib arm than in the standard of care arm. This would also include grade 2 hemorrhage if considered significant by the treating physician in collaboration with PI.
- If the percentage of grade 4 all-cause adverse events is at least 15% higher in the ibrutinib arm than in the standard of care arm
- If the percentage of grade 5 treatment-related adverse events is at least 5% higher in the ibrutinib arm than in the standard of care arm

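### Baseline oxygen requirement, recorded at screening and closest to the endpoint, is not named as a stratification factor or covariate, and the deciding test is unadjusted.

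*Combined protocol and SAP*

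**What the plan says.** - **Entry (Section 5.1, item 4).** Pulmonary involvement can be met in several ways, joined by the word or: "presence of infiltrates on chest X-ray or CT scan or need for supplemental oxygen" below 8 L by nasal cannula, or a room-air oximetry criterion. Patients on room air and patients already on oxygen are enrolled together.
- **Data (Section 12, footnote B).** Vital signs, taken from screening on: "Should include Oxygen saturations and O2 requirement".
- **Endpoint (Section 13).** Respiratory failure or death in hospital within 30 days. Most of the qualifying events are steps up in respiratory support.
- **Randomization (Section 13).** 1:1 in permuted blocks, stratified on age (below 60, or 60 and over) and comorbidity (yes or no).
- **Primary test (Section 13, Primary Endpoint Analysis).** Unadjusted one-sided Fisher exact test at 0.20, on all randomized patients.
- **Adjustment (same place).** Sensitivity analysis only, by logistic regression "adjusting for stratification factors and other important variables such as type of cancer or more refined categories of standard of care therapy". The Secondary Endpoints paragraph also plans logistic models of the primary endpoint on unspecified baseline characteristics, with arm included, described as largely descriptive.

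**The concern.** A patient who enters on several litres of oxygen is closer to high-flow oxygen or ventilation than one who enters with infiltrates on room air. With about 30 patients per arm and nothing balancing this factor, the arms can differ noticeably at the start. The unadjusted comparison then partly measures which arm began sicker. At a one-sided 0.20 level, a few such patients can decide whether a promising signal is declared.

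The stratification may balance less than it appears to. The Appendix C comorbidity list includes active malignancy, and inclusion criterion 2 requires active cancer. Read literally, every patient is a comorbidity yes, and age is the only working stratification factor.

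The adjusted model does not settle the matter. Its covariate list is given by example, so oxygen could be added once an imbalance has been seen, which is the choice that pre-specification is meant to remove.

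**Working it through.** **1. The plan's own figure.** Inputs from Section 13: "we assume that the event rate is 40% with standard care and that the event rate can be reduced to 15" percent; "constraining the one-sided type I error to 20" percent; "With 60 patients and using a standard group sequential design, there is 82.8% power"; "adjustment for small sample sizes with the Casagrande-Pike-Smith correction"; one futility look at half the patients.
- Correction: n = (n′/4)·[1 + √(1 + 4/(n′d))]². With n = 30 and d = 0.25, n′ = 22.53 per arm.
- Standard errors: null √(2 × 0.275 × 0.725/22.53) = 0.133; alternative √((0.40 × 0.60 + 0.15 × 0.85)/22.53) = 0.128.
- Final-analysis limit: (0.25 − 0.8416 × 0.133)/0.128 ≈ 1.08, which gives 86.0% power without the futility look.
- Interim limit: 0.25/(0.128 × √2) ≈ 1.38. The bivariate normal with correlation √0.5 gives 82.77%, against 82.8% stated. The design figure reproduces.

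**2. Overall false-positive rate.** Enumerating Fisher's rejection region at 40% v 40%, 30 per arm, gives 0.123 (0.119 with the futility look). With a prognostic oxygen factor left unstratified and averaged over randomization, it is 0.121–0.123. There is no inflation.

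**3. What an imbalance does: exact enumeration.** Assumed: half of patients on oxygen, 40% event rate overall, no drug effect, 12/30 on oxygen in the ibrutinib arm v 18/30 on control. The expected spurious difference is imbalance × risk difference. With event rates of 55% on oxygen and 25% off it:
- ibrutinib: (12 × 0.55 + 18 × 0.25)/30 = 11.1/30 = 37%
- control: (18 × 0.55 + 12 × 0.25)/30 = 12.9/30 = 43%

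That is 6 points (0.20 × 0.30) in ibrutinib's favour. The false-positive rates of Fisher's test are:

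| Event rate on / off oxygen | Odds ratio | Balanced | 20-point imbalance | Ratio |
|---|---|---|---|---|
| 50% / 30% | (0.5/0.5)/(0.3/0.7) = 2.3 | 0.118 | 0.194 | 1.6 |
| 55% / 25% | (0.55/0.45)/(0.25/0.75) = 3.7 | 0.111 | 0.235 | 2.1 |
| 60% / 20% | (0.6/0.4)/(0.2/0.8) = 6.0 | 0.101 | 0.280 | 2.8 |

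A Mantel-Haenszel test stratified by oxygen stays at about 0.20 in the three imbalanced cases (about 0.13 with continuity correction). The chance of a 20-point imbalance favouring ibrutinib is about 10% at 30 per arm, 7% at 33 and 2% at 60.

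**4. A 15-point threshold: simulation.** Assumed: 60% on oxygen, 60% aged 60 or over, age odds ratio 3, control rate 40%, blocks of 4 within age, no drug effect. Since 0.15 × 30 = 4.5, the arms must differ by at least 5 patients. The exact binomial probability is 23.5% in either direction, or 11.8% favouring ibrutinib. The ranges below cover repeated runs at 60 and 66 patients.

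| Oxygen odds ratio | Imbalance favours | Fisher | Exact, stratified by age and oxygen |
|---|---|---|---|
| 4 | ibrutinib | 24–26% | 12–14% |
| 3 | ibrutinib | 20–23% | 12–14% |
| 2 | ibrutinib | 17–19% | 12–13% |
| 4 | control | 3–4% | 12–13% |
| 2–3 | control | 7% | 11–14% |

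Across all runs the stratified test lies at about 12–15% when the imbalance favours ibrutinib. Over all randomizations the two tests have similar error, about 12% for Fisher and 13% for the stratified test. Power differs by about −1 to +2 points.

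These simulations include neither the futility stop nor an increase to 120 patients. In the 60% / 20% case of step 3, the futility look moves a simulated 0.278 only to 0.270.

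**The case against.** An unadjusted test is valid under randomization. Its long-run error is well below 20%, and harmful and helpful imbalances are equally likely. The trial seeks a signal, and stratifying gains almost no power. All of this stands, and it rules out three stronger readings that a reader might infer.

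- *That the trial's type I error is inflated.* It is not; it stays near 12%.
- *That an imbalance doubles the false-positive rate.* This holds only given a sizeable imbalance favouring ibrutinib and an oxygen odds ratio of about 3–4, and only relative to Fisher's actual rate of about 12%. At odds ratio 2 the ratio is about 1.5. Against the nominal 20%, a rate of 24–26% is 1.2 to 1.3 times, and 17–19% is below it.
- *That oxygen is left out of every planned adjustment.* The Section 13 covariate list is open-ended, and the baseline-characteristic models could include oxygen. The supportable statement is that oxygen is not named.

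It is also fair that changing the primary test is more than a wording change, because the conditional-power zones and scenario tables rest on an unstratified comparison.

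The conditional point remains. The sponsor runs one trial and will see its baseline table. If that table favours ibrutinib on oxygen, the long-run error rate will not reassure a reader about that result, and the descriptive models do not govern the decision.

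**Conclusion.** The concern holds as an omission with a conditional cost, and it is worth correcting; it does not invalidate the design. When the imbalance favours ibrutinib by 15 points or more, the unadjusted test's false-positive rate rises from about 12% to between 17% and 26% across assumed odds ratios of 2 to 4. The opposite imbalance lowers it to about 3–7%. Stratifying by age and oxygen holds it at about 11–15% in both directions.

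The textual finding is firm. The size is not: oxygen prevalence (50% or 60%), the oxygen and age odds ratios and the age mix are all assumed, since the documents give no event rate or prevalence by baseline oxygen. The problem shrinks if the trial grows towards 120 patients.

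**What to change.** **Preferred.** Make the primary test an exact stratified (Mantel-Haenszel type) test by age group and baseline oxygen (none v any, from the screening record) at the same one-sided 0.20 level. Report the unadjusted Fisher test as a sensitivity analysis. Base the interim conditional power on the same statistic, so that the interim zones and the final decision agree. Clarify the comorbidity definition at the same time. As written it may not separate patients, which is why it is left out here; adding it would double the four strata to eight, averaging 60/8 = 7.5 patients each.

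**If Fisher stays primary.** Name baseline oxygen now as the first covariate in the adjusted sensitivity analysis. This removes the after-the-fact choice but leaves the conditional error of the primary decision unchanged.

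**Cost.** No new data. Strata are sparse at 60 patients (60/4 = 15 on average), which an exact test can handle. Power changes by about −1 to +2 points, and the interim calculations need a minor re-run. Stratifying later randomizations on oxygen would also help, but it means altering the randomization system; the analysis change does not depend on it.

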Enrollment to this dose level will stop if 2 of the first 3 evaluable patients or if at least 33% of subsequent evaluable patients (i.e, 2/6, 3/9, or 4/12) have DLT. If unacceptable toxicity is observed, Ibrutinib will decrease to 280 mg daily, and another 12 patient lead-

in will be evaluated at this lower dose level following the same stopping rules. If acceptable toxicity is observed, the study will proceed to the randomized component. Patients who do not receive 14 days of Ibrutinib for reasons other than toxicity or DLT will be replaced for the purposes of the safety and tolerability assessment.

Randomized Phase 2

The main study is a randomized, double-blind placebo-controlled trial. The primary endpoint of the phase 2 component is the proportion of randomized patients with respiratory failure or death during hospitalization for COVID-19 infection within 30 days of registration. Respiratory failure is defined as any of the following: 1) endotracheal intubation and mechanical ventilation, 2) extracorporeal membrane oxygenation, 3) high-flow nasal cannula oxygen delivery (i.e., reinforced nasal cannula delivering heated, humidified oxygen with fraction of delivered oxygen ≥ 0.5 and flow rates of ≥ 30 l/min), noninvasive positive pressure ventilation, or 4) clinical diagnosis of respiratory failure without initiation of one of above measures only when clinical decision-making is driven solely by resource limitation or if patient has DNI (Do Not Resuscitate) status. Patients will be randomized to each treatment arm in a 1:1 ratio utilizing a permuted block schedule. Randomization will be stratified on age (<60 years vs ≥ 60 years) and presence of comorbidities (yes vs no) (comorbidities defined in Appendix C).

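### The sensitivity analysis for clinically diagnosed respiratory failure removes randomized patients because of their outcome, and any later in-hospital deaths with them

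*Combined protocol and SAP*

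**What the plan says.** All statements are in Section 13 (Randomized Phase 2 and Primary Endpoint Analysis).

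- The primary endpoint is "the proportion of randomized patients with respiratory failure or death during hospitalization for COVID-19 infection within 30 days of registration".
- One component of respiratory failure is a "clinical diagnosis of respiratory failure without initiation of one of above measures only when clinical decision-making is driven solely by resource limitation". A DNI order is the second route into this same component.
- The primary analysis keeps everyone: "All randomized patients will be included in the primary endpoint analysis and analyzed in the treatment arm to which they were randomized (ITT population").
- If events of the clinical-diagnosis kind occur, "a sensitivity analysis will compare arms excluding patients with these events".
- The next sentence reads: "Sensitivity analyses will be performed for the ITT population and for eligible patients who receive their assigned therapy without a major protocol violation".

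Nothing in the plan keeps such a patient in the denominator, recodes the patient as a non-event, or counts the patient as an event on a later death.

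**The concern.** The purpose of the check is sound. One component of the composite depends on judgement, and a reader will want to know whether the result depends on it. That calls for disregarding the component. The plan instead disregards the patients.

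Two things follow. First, having the event is a post-randomization outcome, so the remaining groups are no longer the randomized groups, and each arm's denominator falls by its own number of such events. Second, these patients are in respiratory failure without any of the listed support measures, so it is reasonable to expect some of them to die in hospital, although the documents give no figure. Such a death is an objective primary event in its own right, and the rule discards it. A check meant to isolate the softest component can therefore also remove the hardest one.

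The rule also conflicts with the sentence that follows it. An analysis that deletes randomized patients by outcome is not an analysis of the ITT population, so the two sentences cannot both be followed as written.

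At stake is whether this check can be trusted to confirm or question the primary result. With about 33 patients per arm and a threshold of 0.20, a few patients can change its message.

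**Working it through.** **Plan's own figure.** Inputs from Section 13: 40% vs 15%, 60 patients (30 per arm), one-sided alpha 0.20, Casagrande-Pike-Smith correction, futility stop at half the patients if the ibrutinib rate is higher.

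- Effective size per arm: n′ = n(1 − 1/(nd))² = 30 × (1 − 1/7.5)² = 22.53, with d = 0.25.
- Variances: unpooled 0.15×0.85 + 0.40×0.60 = 0.3675; pooled 2×0.275×0.725 = 0.39875.
- Mean of the final statistic: 0.25/√(0.3675/22.53) = 1.958. Critical value: 0.8416 × √(0.39875/0.3675) = 0.877.
- P(interim Z > 0 and final Z > 0.877), with correlation √0.5, is 0.828.

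This matches the stated 82.8%. The sensitivity rule does not enter the calculation.

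**Effect of the rule on one arm.** Let n be the patients randomized, e the primary events, k the clinical-diagnosis events, and m those among the k who also die in hospital or have an objective component.

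- Rule as written: (e − k)/(n − k).
- Everyone kept, component disregarded: (e − k + m)/n.
- First minus second: k(e − k)/[n(n − k)] − m/n.

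The first term (smaller denominator) raises the arm's rate. The second (lost objective events) lowers it. The two oppose each other.

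**Illustration 1.** The documents give no expected number of these events, so all counts here and below are assumptions. They use 33 per arm, from the accrual goal of 66, and are given as control vs ibrutinib. Primary result 13/33 vs 5/33, of which 4 vs 1 are clinical-diagnosis events.

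| Analysis | Control | Ibrutinib | Difference |
|---|---|---|---|
| Exclusion as written | 9/29 = 31.0% | 4/32 = 12.5% | 18.5 points |
| Everyone kept, none of the five died | 9/33 = 27.3% | 4/33 = 12.1% | 15.2 points |
| Everyone kept, 3 of the 4 control patients died | 12/33 = 36.4% | 4/33 = 12.1% | 24.2 points |

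In the control arm the denominator term is 4×9/(33×29) = 3.8 points, and three lost deaths are 3/33 = 9.1 points. The net is −5.3 points, which is 31.0% against 36.4% before rounding. In the ibrutinib arm the denominator term is 1×4/(33×32) = 0.4 points. Exclusion therefore overstates the difference by about 3.4 points if nobody died and understates it by about 5.7 if three control patients died. All three one-sided Fisher p-values (0.073, 0.11, 0.021) are below 0.20.

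**Illustration 2: p crosses 0.20 downwards.** Primary 12/33 vs 9/33, p = 0.299, with 1 vs 3 clinical-diagnosis events.

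- Exclusion: 11/32 vs 6/30, p = 0.163.
- Everyone kept, 1 vs 2 deaths counted: 12/33 vs 8/33, p = 0.211.
- Everyone kept, no deaths: 11/33 vs 6/33, p = 0.130. The lost deaths, not the denominators, make the difference here.

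**Illustration 3: p crosses 0.20 upwards.** Primary 13/33 vs 7/33, p = 0.090, with 3 vs 0 such events.

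- Exclusion: 10/30 vs 7/33, p = 0.212.
- Everyone kept, two deaths counted: 12/33 vs 7/33, p = 0.138.

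**Illustration 4: balanced removal.** Primary 12/33 vs 9/33 with 2 vs 2 such events.

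- Exclusion: 10/31 vs 7/31, p = 0.285.
- Everyone kept, one death per arm counted: 11/33 vs 8/33, p = 0.294.

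**The case against.** The strongest case against acting is that very little depends on this analysis. It is run only if such events occur. A DNI patient who receives high-flow oxygen or noninvasive ventilation already has an objective component, so the affected group may be tiny or empty. The promising-signal decision rests on the ITT Fisher test, where these patients and their in-hospital deaths count, and overall survival is estimated by arm as well. The crossings of 0.20 need imbalanced, chosen counts. All of this stands, and it limits the point to a minor one.

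The wording may also be loose. Section 13 describes these events as lacking an objective measure, and it places sensitivity analyses in the ITT population, so the authors may not have meant to drop patients who die. That is possible, but the operative instruction excludes patients and no sentence brings them back.

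A reader might infer that exclusion tilts the check towards ibrutinib, because the hypothesis predicts more such events in the control arm. The documents do not support a direction. Illustration 1 follows exactly that pattern, yet exclusion favours ibrutinib only while few of the excluded control patients died. With three such deaths it works against ibrutinib.

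**Conclusion.** The sentence is wrong as written. It selects on a post-randomization outcome, reduces denominators by arm, discards objective deaths among the excluded patients, and conflicts with the stated ITT population. The fault follows from the text and needs no assumption. The size does rest on assumptions: the number of clinical-diagnosis events, their split by arm, and the deaths among them are not in the documents. In the illustrations the error in the difference runs from an overstatement of about 3.4 points to an understatement of about 5.7. The p-value can end on the wrong side of 0.20 in either direction, or hardly move when removal is balanced.

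A reader might also infer that the trial's conclusion or power is compromised. It is not: the primary test keeps all randomized patients, and the 82.8% is untouched. The point is minor because the analysis is supportive.

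**What to change.** In Section 13, Primary Endpoint Analysis, replace the exclusion of patients with: *keeping all randomized patients in their assigned arm and disregarding the clinical-diagnosis component; such patients count as events only if they also have an objective respiratory-failure component or in-hospital death within 30 days of registration, otherwise as non-events.*

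Add that the number of clinical-diagnosis events, and of subsequent deaths among those patients, will be reported by arm.

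This costs one sentence and one line in a results table. It uses data already needed for the primary endpoint and changes neither the sample size nor the primary test. It should be settled before unblinding.
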